8.3 Response Definitions

Symptom Response:	To be defined based upon a blinded review of symptom scores (pooled for all influenza-infected subjects without regard to treatment group assignment) that correlate to the time at which subjects report that they return to usual health (a daily global assessment question). Methodology for the correlation will be defined in the Statistical Analysis Plan. Symptom scores must be maintained at the defined level for at least 2 daily diary periods without any symptom relief medication during those 2 daily diary periods.
Time of Symptom Response:	The start of the first daily diary period in which Symptom Response is achieved and is maintained for at least 2 daily diary periods without any symptom relief medication during those 2 daily diary periods.
Time to Symptom Response:	Time (hours) from first dose to the Time of Symptom Response.
Ability to Perform All Normal Activities:	Subject reports a score of 10 on the 0-10 scale for ability to perform normal activities, which is maintained for at least 2 daily diary periods without symptom relief medication during those 2 daily diary periods
Time of Ability to Perform All Normal Activities:	The time of the first daily diary entry in which the subject reports a score of 10 on the 0-10 scale for ability to perform normal activities, which is maintained for at least 2 daily diary periods without symptom relief medication during those 2 daily diary periods
Time to Ability to Perform All Normal Activities:	Time (hours) from first dose to the Time of Ability to Perform All Normal Activities
Individual Symptom Response:	For each individual symptom (n=32), a score of \leq the maximum response value specified in the Symptom Response definition maintained for at least 2 daily diary periods without symptom relief medication during those 2 daily diary periods
Time of Individual Symptom Response:	The start of the first daily diary period in which the Individual Symptom Response is achieved and is maintained for at least 2 daily diary periods without symptom relief medication during those 2 daily diary periods
Time to Individual Symptom Response:	Time (hours) from first dose to Time of Individual Symptom Response
FLU-PRO Domain Response:	For each individual domain (n=6), each item scored \leq the maximum response value specified in the Symptom Response definition

maintained for at least 2 daily diary periods without symptom relief medication during those 2 daily diary periods

Time of FLU-PRO Domain Response:

For each domain, the start of the first daily diary period in which the FLU-PRO Domain Response is achieved and is maintained for at least 2 daily diary periods without symptom relief medication during those 2 daily diary periods

Time to FLU-PRO Domain Response:

Time (hours) from first dose to FLU-PRO Domain Response for each domain

Resolution of Acute Febrile Illness:

Oral temperature is recorded by the patient as $<100.4^{\circ}\text{F}$ ($<38^{\circ}\text{C}$) and symptom scores for each of “body aches or pains”, “chills or shivering”, “felt cold”, “felt hot” and “sweating” are 0 or 1 and remain so throughout 2 daily diary periods without symptom relief medication during those 2 daily diary periods

Time to Resolution of Acute Febrile Illness:

Time (hours) from first dose to resolution of acute febrile illness.

Return to Usual Health:

“Yes” response to the daily FLU-PRO global assessment question, “Have you returned to your usual health today?” maintained for at least 2 daily diary periods without symptom relief medication during those 2 daily diary periods

Time of Return to Usual Health:

The time of the first daily diary entry in which Usual Health is achieved and is maintained for at least 2 daily diary periods without symptom relief medication during those 2 daily diary periods

Time to Return to Usual Health:

Time (hours) from first dose to Time of Return to Usual Health

8.4 Statistical Methodology

The statistical methodology is described briefly below and will be described in detail in the Statistical Analysis Plan.

8.4.1 Efficacy Analyses

Efficacy analyses will be based on a population consisting of all subjects that received at least one dose of study drug and had laboratory-documented influenza infection (infected intent-to-treat or ITTI population). Laboratory-documented influenza infection is defined by identification of influenza virus in nasopharyngeal secretions by RT-PCR or viral culture at baseline, day 2 or day 3.

There will be one primary efficacy analysis:

- Time to Symptom Response for the NTZ treatment group will be compared to that of the placebo treatment group using a stratified Gehan-Wilcoxon test ($\alpha = 0.05$) stratified by (1) time since symptom onset for each subject at enrollment (≥ 24 hours, $>24 - 36$ hours, >36 hours) and (2) whether the subject received seasonal influenza vaccination after August 1, 2018. Subjects without a Symptom Response being recorded will be treated as censored as of their last diary without a documented Symptom Response.

If the primary analysis is significant at the 0.05 level, a key secondary efficacy analysis will be formally evaluated at the 0.05 level as follows:

- Time to Ability to Perform All Normal Activities for the two treatment groups will be compared using a stratified Gehan-Wilcoxon test ($\alpha = 0.05$) stratified by (1) time since symptom onset for each subject at enrollment (≥ 24 hours, $>24 - 36$ hours, >36 hours) and (2) whether the subject received seasonal influenza vaccination after August 1, 2018. Subjects without an Ability to Perform All Normal Activities response being recorded will be treated as censored as of their last diary without a documented Ability to Perform All Normal Activities response.

If both the primary analysis and the key secondary efficacy analysis are significant at the 0.05 level, another secondary efficacy analysis will be formally evaluated at the 0.05 level as follows:

- Proportions of subjects experiencing one or more complications of influenza including pneumonia, otitis media, bronchitis, sinusitis, worsening of pre-existing health conditions, systemic antibiotic use for infections secondary to influenza infection, hospitalization due to influenza or complications of influenza and death will be compared between the treatment groups using a Fisher's exact test ($\alpha = 0.05$).

A third secondary analysis will be performed as follows:

- The primary efficacy analysis will be repeated using only items from the four FLU-PRO domains (Body/Systemic, Throat, Chest/Respiratory and Nose) that correspond to the seven symptoms included in the traditional PRO instrument (feverishness, myalgia, headache, fatigue, sore throat, nasal obstruction and cough). For this secondary analysis, we will derive the Symptom Response definition in the same manner as for deriving the Symptom Response definition used in the primary analysis (after removing the Eye and Gastrointestinal symptoms).

Exploratory analyses will be performed as follows:

- For each of the 32 individual FLU-PRO symptoms, Time to Individual Symptom Response for the NTZ and placebo treatment groups will be compared using the Gehan-Wilcoxon test.
- For each of the 6 FLU-PRO domains, Time to FLU-PRO Domain Response for the NTZ and placebo treatment groups will be compared using the Gehan-Wilcoxon test.
- Time to Resolution of Acute Febrile Illness for the NTZ and placebo treatment groups will be compared using the Gehan-Wilcoxon test.
- Time to Return to Usual Health for the NTZ and placebo treatment groups will be compared using the Gehan-Wilcoxon test.
- Changes in influenza TCID₅₀ viral titers from baseline to day 2 and from baseline to day 3 for the NTZ and placebo treatment groups will be compared using a t-test.
- For subjects with laboratory-confirmed influenza, the proportions of subjects with influenza virus detected by culture in nasopharyngeal swabs collected at each of days 2, 3 and 7 will be compared for the two treatment groups using a Fisher's exact test.

Sensitivity analyses for the primary endpoint will include:

- Repeat the primary efficacy analysis, assigning a Time to Symptom Response of 21 days for subjects that discontinue prior to day 21 without achieving Symptom Response.
- Repeat the primary efficacy analysis for a “per protocol” subset.

8.4.2 Influenza Antibody Titer Analysis

For subjects with laboratory-confirmed influenza at baseline by culture or RT-PCR, changes in influenza antibody titers from baseline to day 22 will be analyzed by comparison of means as well as proportions of subjects seroprotected (day 22 antibody titer ≥ 40) and seroconverted (day 22 antibody titer $>4x$ baseline titer) at day 22. Means will be compared using a t-test, and proportions will be compared using a Fisher’s exact test.

8.4.3 Population Pharmacokinetics Analysis

On day 3, the plasma samples will be collected before the morning dose (at the trough). This data will allow for analysis of relationships between trough plasma concentrations and clinical and virologic response.

Day 3 trough plasma concentrations of tizoxanide and tizoxanide glucuronide will be summarized descriptively for each of the treatment groups. Exploratory analyses will be conducted to evaluate relationships between plasma concentrations and age, race, gender, body weight, body mass index, concomitant medications, changes in viral titer over time, time from first dose to Symptom Response and adverse events.

8.4.4 Safety Analyses

All randomized subjects who receive the study medication will be evaluated for drug safety. Safety analyses will be done descriptively.

9 INVESTIGATIONAL PRODUCTS

9.1 Drug Regimens, Administration and Duration

Group 1 (NTZ): Subjects will receive two NTZ 300 mg tablets b.i.d. with food (< 1 hour after food intake) for 5 days.

Group 2 (Placebo): Subjects will receive two placebo tablets b.i.d. with food (< 1 hour after food intake) for 5 days.

The food prior to drug intake should preferably be a high-fat meal, but at minimum a cereal bar.

9.2 Identity of Investigational Products

NTZ 300 mg and placebo tablets were manufactured for Romark Laboratories, L.C. by [REDACTED] in the United States. The active formulation for this study is a yellow, film-coated tablet that contains 300 mg NTZ plus standard excipients. The placebo tablet will have the same appearance and inactive ingredients as the active tablet.

9.3 Packaging and Labeling

NTZ or placebo tablets will be packaged for each patient in a white HDPE bottle, each containing 20 tablets. The subjects will take two tablets at each dosing time point. The bottles will be stored at room temperature and will bear a label with the following information:

20 Tablets Lot:	Study N RM08-3004 Treatment N : XXXX Principal Investigator:
Take 2 Tablets by Mouth with Food Twice Daily Caution: New Drug-Limited by Federal Law to Investigational Use STORE AT ROOM TEMPERATURE • DO NOT USE BEYOND END OF STUDY KEEP OUT OF REACH OF CHILDREN Study Sponsor: The Romark Institute for Medical Research [REDACTED]	

9.4 Drug Accountability

Medication will be dispensed at baseline. Medication compliance will be reviewed with each subject during the Day 2-5 Telephone Monitoring. At the day 7 visit, subjects will be asked to return the bottle in which the medication was dispensed along with any unused medication.

The Investigator or designee is required to maintain adequate records of the disposition of all study drug, including dates, quantity and use by subject. Unused supplies must be returned to the Sponsor.

9.5 Subject Compliance

Subject compliance with the protocol will be checked by the Investigator and recorded in the EDC system at each visit.

Subjects will be considered non-compliant (major protocol violation) if they have missed more than two doses of the study medication during the first three days of the study or if they take any prohibited/disallowed medication. Non-compliance will not be cause for discontinuation of subject participation in the study.

9.6 Disallowed Medication

The following medications will not be allowed during the study: any antiviral medication for flu or any prescription or non-prescription medications classified as (i) expectorants and cough preparations, (ii) analgesics and antipyretics or (iii) antihistamines (American Hospital Formulary Service (AHFS) classification). As an exception to this rule, subjects will be allowed to use acetaminophen as necessary for fever if oral temperature is $\geq 100.4^{\circ}\text{F}$ (38°C).

Medications for pre-existing conditions that are not excluded (see exclusion criteria) should be continued as prescribed. The use of such medication will be recorded in the EDC system.

10 ADVERSE EVENTS

The term “adverse event” is defined for purposes of this study as any unwanted physical, psychological or behavioral change experienced by a subject during the course of the study and after taking the first dose of study medication regardless of its severity or relation to the study. Adverse events may include symptoms, signs, unexpected worsening of pre-existing conditions, clinically significant changes in laboratory values, diseases and syndromes, and significant and unexpected failures of pharmacological action of other medications. Symptoms of influenza (i.e., those captured in the FLU-PRO Questionnaire) and complications of influenza (e.g., pneumonia, otitis media, bronchitis, sinusitis) shall not be reported as adverse events unless

there is a causal relationship between the study medication and the event. These symptoms and complications will be analyzed separately from adverse events as they are study endpoints.

Bacterial pneumonia, acute bacterial otitis media and acute bacterial sinusitis will be reported as complications of influenza only if the following criteria are satisfied:

Bacterial pneumonia:

1. At least two of the following symptoms: difficulty breathing, cough, production of purulent sputum, chest pain
2. At least two of the following vital sign abnormalities: fever, hypotension, tachycardia, tachypnea
3. At least one of the following findings: hypoxemia, clinical evidence of pulmonary consolidation, elevated white blood cell count or leukopenia
4. Chest radiograph findings of new infiltrates in a lobar or multilobar distribution.
5. Microbiologic criteria: appropriate sputum specimen with fewer than 10 squamous epithelial cells and more than 25 polymorphonuclear cells per low power field

Acute bacterial otitis media:

1. Symptoms of ear pain or earache, ear fullness or decreased hearing
2. One or more of the following otoscopic findings performed by a clinician experienced in otoscopy:
 - Bulging or fullness of the tympanic membrane (convexity of the plane of the eardrum), with loss of anatomic landmarks on visualization,
 - Opacification of the tympanic membrane regardless of color,
 - Erythema of the tympanic membrane, or
 - Abnormal tympanic membrane mobility on biphasic pneumatic otoscopy; a tympanic membrane in the neutral position or retracted is not sufficient evidence of acute bacterial otitis media because these findings are not specific enough to distinguish the disease from otitis media with effusion

Bacterial sinusitis:

1. At least two of the following symptoms:
 - Maxillary tooth pain (unilateral findings can be more specific)
 - Facial pain (unilateral findings can be more specific)
 - Frontal headache
 - Purulent nasal discharge (unilateral findings can be more specific)
 - New onset fetor oris (bad breath)
 - Morning cough
 - Nasal obstruction
2. At least one of the following signs:
 - Purulent secretions from sinus ostia on examination
 - Abnormal sinus transillumination
 - Pain on palpation over sinuses
 - Facial swelling
3. Radiographic findings consistent with acute sinusitis

Adverse events will be recorded on the appropriate EDC forms throughout the study, and the severity of each adverse event will be graded on a four point scale: mild, moderate, severe, or life threatening (See Appendix II). The duration of the adverse event and relationship to the study drug will also be recorded. All adverse events must be followed until their resolution or stabilization even beyond the planned study period.

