3 STUDY DESIGN

The study will be a multicenter, randomized, double-blind trial to evaluate the efficacy of NTZ compared to placebo in treating uncomplicated influenza. Subjects will be selected according to the inclusion and exclusion criteria listed below. The study is designed to enroll at least 600 subjects (up to 700 maximum) with laboratory-confirmed influenza. Total enrollment required to achieve this number is expected to be approximately 800 to 1200 subjects. Prior to screening for inclusion in the study, informed consent will be obtained.

Immediately after completion of informed consent, screening, and enrollment in the study, two baseline nasopharyngeal swabs will be collected for viral culture and RT-PCR. A blood sample will be collected for laboratory safety tests and anti-influenza antibodies, and a urine sample will be collected for laboratory safety tests. Subjects will receive instruction on completion of their electronic diaries, concomitant medications and attending follow-up visits.

Then subjects will be randomized 1:1 to one of the following groups:

- Group 1 (NTZ): Two NTZ 300 mg tablets b.i.d. for 5 days
- Group 2 (Placebo): Two placebo tablets b.i.d. for 5 days

The medication will be taken twice daily with food (preferably a high-fat meal, but at minimum a cereal bar). The first dose will be taken with food in the physician's office under the observation of the Principal Investigator or a member of the Investigator's staff. The second dose will be taken by the subject as close as possible to 12 hours after the first dose.

A nurse or other study personnel will visit each subject (or the subject will return to the clinic) on study days 2 and 3 to collect two nasopharyngeal swabs, to review patient diaries, and to review symptoms and screen for influenza-related complications including sinusitis, otitis, bronchitis, pneumonia and central nervous system disease. Subjects will be referred for immediate care as needed based on the screening. A blood sample for pharmacokinetics will also be collected on study day 3. These day 2 and 3 visits will occur at approximately

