the same time of day that the subject took his/her first dose of study medication (roughly 24 and 48 hours post-first dose). On day 3, the blood sample for pharmacokinetics will be collected before the dose. The nasopharyngeal swabs will be used to evaluate quantitative changes in viral shedding. The blood samples will be used to evaluate relationships between pharmacokinetics and virologic or clinical response. Study sites or subjects may opt out of the day 2 and day 3 visits due to site staffing, patient availability or other practical considerations or preferences; nevertheless, at least 75% of subjects enrolled in the trial are expected to complete the day 2 and day 3 visits and related procedures (for viral kinetics and pharmacokinetics).

A study physician, nurse or other site personnel will make daily telephone calls to subjects for the first five days of dosing to review symptoms and screen for influenza-related complications including sinusitis, otitis, bronchitis, pneumonia and central nervous system disease. Subjects will be referred for immediate care as needed based on the screening. [Note: In lieu of a telephone call, this information may be obtained during the day 2 or 3 office or home visits (see the preceding paragraph).] The study sites and subjects will be blinded from virology laboratory data until after study day 22 or, if earlier, until the subject is discontinued from the study. During the study period, each subject will be presumed to have influenza infection, and any worsening of symptoms or complications will be presumed to be influenza-related.

Subjects will return to the clinic on days 7 and 22 for post-treatment follow-up, including two nasopharyngeal swabs, drug accountability, reporting of adverse events and complications of influenza. Blood and urine samples for laboratory safety tests will be collected at day 7, and a blood sample for anti-influenza antibodies will be collected on day 22. A nurse or other study personnel will review the electronic patient diary entries daily (synchronized to a web-based data system) to ensure contemporaneous and complete recording of diary data. Subjects will maintain the electronic patient diaries until study day 22. Any visits that do not occur on the prescribed date, or within 1 day of that date in the case of the day 7 visit or within 3 days after that date in the case of the day 22 visit, will be recorded as protocol deviations.

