8 STATISTICAL CONSIDERATIONS

8.1 Sample Size Calculation

As described in section 7.3 below, the Symptom Response definition for this study will be derived from the subjects' FLU-PRO questionnaire responses. The FLU-PRO-derived endpoint is expected to track very closely to return to usual health status (a daily yes/no question in the FLU-PRO questionnaire). Patient-reported outcomes for time to return to usual health status have been shown to track very closely with time to ability to perform 100% of usual activities.^{27,28,29} We assume, therefore, that the cumulative distributions of time to Symptom Response for the placebo treatment group will closely reflect historical data (Romark studies RM08-3002 and RM08-3003 and oseltamivir studies WV15670 and WV15671) for time from first dose until the subjects report that they are able to perform 100% of usual activities. Based upon data from Romark studies RM08-3001, RM08-3002 and RM08-3003, we assume that treatment with NTZ should result in reduction of at least 40 hours in median time to symptom response with differences being less at the first

quartile and greater at the third quartile. Based upon this historical data, the following curves have been developed for determining sample size.

Based upon these curves, a sample size of 552 subjects with laboratory-confirmed influenza (i.e. 276 for each of the 2 groups) will provide 90% power to detect a statistically significant difference in the survival distributions between NTZ and placebo groups (2-sided alpha of 0.05). This calculation was performed for the Gehan rank test using SAS PROC POWER (SAS 9.4) with the curves shown above (proportion not recovering by the end of each day was used as input) and censoring at day 21 (hour 504). Assuming that 8% of subjects will have incomplete data, we arrive at a sample size of 600 subjects in total, 300 per treatment group to yield at least approximately 550 with complete data (all 600 subjects will be included in the primary analysis with subjects with incomplete data censored as of their last entry).

Based upon these calculations, the study will enroll at least 600 subjects with laboratory-confirmed influenza up to a maximum of 700 subjects with laboratory-confirmed influenza. We estimate that this will require enrollment of 800 to 1,200 subjects in total assuming a flu-positive rate between 50% and 75%.

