10.4.2 Proportion of Subjects Experiencing Complications of Influenza

Variables Used for the Analysis

The analysis will require the following variables:

Variable	Source	Format/Notes
Complications of influenza	CRF	Investigators will designate an adverse event as a complication of influenza if the event meets protocol-specified criteria

Analysis

Proportions of subjects experiencing one or more complications of influenza will be compared between the treatment groups using a Fisher’s exact test.

Analysis Population(s):	Confirmed Influenza
Derived Variables:	None

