11. SAFETY

11.1 Safety Tables and Figures

Unless otherwise specified, all safety tables will be based on the All Treated population and present data by treatment group.

Adverse events summary tables will use the following algorithms for counting subject events:

- Preferred term: Each subject will be counted once within each unique preferred term at the maximum grade.
- System organ class: Each subject is counted only once at the maximum grade at each system organ class level.
- Any event: Each subject with an event is counted only once at the maximum grade.

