14.3.1.7	Number and Percent of Subjects with Treatment Emergent Serious Adverse Events by System Organ Class and Preferred Term	Table	All Treated

Display Number	Title	Type	Analysis Population
14.3.1.8	Number and Percent of Subjects with Treatment Emergent Adverse Events Leading to Study Withdrawal by System Organ Class and Preferred Term	Table	All Treated
14.3.2.1	Summary of Hematology Laboratory Results and Changes from Baseline	Table	All Treated
14.3.2.2	Change in Hematology Laboratory Results Over Time: Shift Table	Table	All Treated
14.3.3.1	Summary of Serum Biochemistry Laboratory Results and Changes from Baseline	Table	All Treated
14.3.3.2	Change in Serum Biochemistry Laboratory Results Over Time: Shift Table	Table	All Treated
14.3.4.1	Number and Percent of Subjects with Each Urinalysis Result	Table	All Treated
14.3.4.2	Change in Urinalysis Results Over Time: Shift Table	Table	All Treated
14.3.5.1	Summary of Vital Signs Results and Change from Baseline	Table	All Treated
14.3.5.2	Change in Vital Signs Results Over Time: Shift Table	Table	All Treated
14.3.6.1	Summary of Physical Examination Results by Category	Table	All Treated
14.3.6.2	Number and Percent of Subjects with Physical Examination Changes from Normal at Baseline to Abnormal by Category	Table	All Treated
Listings			
16.1.1	Listing of Discontinued Subjects	Listing	All Treated
16.2.2	Listing of Subjects with Protocol Deviations	Listing	All Treated
16.2.3	Listing of Subjects Excluded from Efficacy Analysis	Listing	Confirmed Influenza
16.2.4.1	Listing of Demographic Data	Listing	All Treated
16.2.4.2	Listing of Baseline Disease Characteristics	Listing	All Treated
16.2.4.3	Listing of Prior Medication	Listing	All Treated
16.2.4.4	Listing of Concomitant Medication	Listing	All Treated
16.2.4.5	Listing of Medical History	Listing	All Treated
16.2.4.6	Listing of Concomitant Diseases	Listing	All Treated
16.2.5	Listing of Treatment Exposure Data	Listing	All Treated
16.2.6.1	Listing of Time to Symptom Response	Listing	Confirmed Influenza
16.2.6.2	Listing of Time to Ability to Perform All Normal Activities	Listing	Confirmed Influenza
16.2.6.3	Listing of Complications of Influenza	Listing	Confirmed Influenza
16.2.6.4	Listing of Time to Modified Symptom Response	Listing	Confirmed Influenza
16.2.6.5	Listing of Time to Individual Symptom Response	Listing	Confirmed Influenza
16.2.6.6	Listing of Time to FLU-PRO Domain Response	Listing	Confirmed Influenza

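### For dosed subjects without confirmed influenza, no by-arm display is assured to show a complication judged unrelated to study drug

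*Protocol*

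**What the plan says.** Protocol section 10 states that "complications of influenza (e.g., pneumonia, otitis media, bronchitis, sinusitis) shall not be reported as adverse events unless" study drug caused them. The reason given is that they are endpoints and are analysed apart from adverse events.

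Protocol 5.1 selects subjects on the eligibility criteria, whatever any local influenza test showed. Protocol section 3 keeps sites blind to virology until after day 22, or until discontinuation if that is earlier. During that time "each subject will be presumed to have influenza infection, and any worsening of symptoms or complications will be presumed to be influenza-related".

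On the analysis side, SAP 10.4.2 says "Proportions of subjects experiencing one or more complications of influenza will be compared between the treatment groups" by Fisher's exact test in the Confirmed Influenza population. SAP 8.1 defines this as treated subjects positive by RT-PCR or culture at baseline, day 2 or day 3. SAP Appendix II gives the same population to table 14.2.4 and to display 16.2.6.3, "Listing of Complications of Influenza". For safety, SAP 11.1 says that, unless otherwise specified, "all safety tables will be based on the All Treated population".

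Two other SAP statements pull the other way. The variable note in 10.4.2 describes a complication as an adverse event that the investigator designates as such. SAP 10.7 says that the efficacy listings cover all subjects.

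**The concern.** Complications are taken out of adverse-event reporting on the ground that another analysis will show them. For subjects without confirmed influenza, that other analysis does not exist. These subjects are dosed by design, because entry rests on symptoms and community circulation.

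The TEAE tables carry the label All Treated. If sites follow Protocol section 10, those tables would leave out pneumonia, bronchitis, otitis or sinusitis judged unrelated to drug. In the unconfirmed subjects, no complications table would make up for it. An imbalance between arms in such events could then go unseen in that part of the treated population. The purpose of a randomized safety table is to compare arms whatever the individual attribution. Protocol section 14 also rules out an independent data monitoring committee, so the planned tables are the main place where such a difference would be noticed.

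**Working it through.** **The rules in sequence**

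1. The site does not know whether the subject has influenza and is told to presume it (Protocol 3).
2. A complication is therefore treated as a complication of influenza. Unless judged drug-caused, it is not reported as an adverse event (Protocol 10). Neither document gives a rule for reclassifying it once virology is released.
3. The complications analysis and table 14.2.4 are limited to Confirmed Influenza (SAP 10.4.2, Appendix II).
4. SAP section 11 and Appendix II contain no complications display in All Treated.

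**Where the documents disagree**

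- Is a complication an adverse event? Protocol 10 says no, unless caused by the drug. SAP 10.4.2 says it is an adverse event carrying a designation, and no SAP text removes designated events from the TEAE tables.
- Who is in the complications listing? SAP 10.7 says all subjects; Appendix II says Confirmed Influenza.
- What happens to a serious complication? Protocol 10.2 requires serious adverse events, and deaths whatever the cause, to go to the sponsor. Hospitalization and death are also components of the complications endpoint (Protocol 8.4.1), which Protocol 10 says is not to be reported as adverse events.

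**How many subjects**

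Protocol section 3 gives the target: "The study is designed to enroll at least 600 subjects (up to 700 maximum) with laboratory-confirmed influenza". Protocol 8.1 gives the total: "800 to 1,200 subjects in total assuming a flu-positive rate between 50% and 75" per cent.

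The plan's own figure reproduces as total = confirmed / positive rate:
- 600 / 0.75 = 800
- 600 / 0.50 = 1,200

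Subjects outside Confirmed Influenza = total - confirmed:
- 800 - 600 = 200, and 200 / 800 = 25%
- 1,200 - 600 = 600, and 600 / 1,200 = 50%

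With 1:1 randomization this is about 100 to 300 per arm.

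The share depends on the assumed positive rate and on the confirmed count. With 700 confirmed inside the same totals it would be 100 / 800 = 12.5% to 500 / 1,200 = 41.7%. In the sponsor's earlier trials (Protocol 1.2.4 to 1.2.6) the positive rates were 257/624 = 41%, 737/1,941 = 38% and 263/324 = 81%. That leaves 59%, 62% and 19% unconfirmed.

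**How many events**

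The documents give no complication rate for uninfected subjects, so the rates below are assumptions. Expected number = rate x 200 to rate x 600:

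| Assumed rate | Subjects with a complication |
|---|---|
| 1% | 2 to 6 |
| 3% | 6 to 18 |
| 5% | 10 to 30 |
| 10% | 20 to 60 |

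At 1%, the chance that at least one such event occurs is 1 - 0.99^200 = 0.87 to 1 - 0.99^600 = 0.998. These are events outside table 14.2.4. How many would also be missing from the TEAE tables depends on which of the conflicting texts is followed.

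**The case against.** A reader might infer that these events appear in no output at all. The documents do not support that, for five reasons.

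- Under SAP 10.4.2 a complication is a flagged adverse-event record. If sites and programmers work that way, it would appear in the All Treated TEAE tables and in adverse-event listing 16.2.7. This is the strongest counter-argument. It shows that the outcome is undetermined, because it contradicts the protocol text that governs what sites report.
- The exclusion in Protocol 10 is limited. Drug-caused events remain adverse events. Bacterial pneumonia, otitis media and sinusitis count as complications only if listed criteria are met. Events that fail the criteria could be reported under the general adverse-event definition, although the text does not say so. Bronchitis has no such criteria.
- Serious events have their own route to the sponsor (Protocol 10.2 and 10.3), and SAE table 14.3.1.7 is All Treated. This does nothing for non-serious events.
- If SAP 10.7 prevails over Appendix II, the complications listing would include unconfirmed subjects. A listing is still not a summary by arm.
- Indirect traces remain in All Treated displays: concomitant medication by ATC class, its listing with indication, and physical examination findings by body system. None of these counts complications.

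It is also fair to say that the 25-50% share is a planning assumption, that the third earlier trial, with the same 40-hour entry window, had only 19% unconfirmed, and that the protocol expects too few complications to show a treatment difference. These points bear on the size of the gap, which they do not close.

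**Conclusion.** The point holds in a limited form. Read as written, Protocol 3 and 10 together with SAP 10.4.2 and table 14.2.4 leave no by-arm display assured to show a complication judged unrelated to drug in a dosed subject without confirmed influenza. Under the planning assumption of a 50-75% positive rate and 600 confirmed subjects, that concerns 200 to 600 subjects (25-50%). The number of events is unknown; 2 to 18 would follow from an assumed rate of 1-3%.

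It would go too far to say that these events are lost or unreported. Sites screen every subject for complications and record them on the case report form, so the weakness lies in classification and display. Nothing here affects the primary analysis, the test in SAP 10.4.2 or the testing hierarchy. The change is worth making because it is cheap and the All Treated safety comparison may otherwise be incomplete.

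**What to change.** - Add to SAP section 11 and Appendix II an All Treated table of complications by arm, giving each component and any complication, split by confirmed versus not confirmed influenza.
- Label listing 16.2.6.3 All Treated in Appendix II, which brings it into line with SAP 10.7.
- Keep the efficacy test in SAP 10.4.2 in Confirmed Influenza.
- Reconcile Protocol section 10 with SAP 10.4.2 on whether a complication is an adverse event, and with Protocol 10.2 on how a serious complication is reported.

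The cost is one descriptive table, one population label and some clarifying text. No new data are needed: screening for complications applies to all subjects, and sites do not know who is confirmed. The table will have low counts and should be read descriptively. SAP section 6 allows revision until the plan is finalized before database lock, so the SAP changes fit within the existing procedure.
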